9.9. Source Documents

Source documents provide evidence for the existence of the patient and substantiate the integrity of the data collected. Source documents are filed at the Investigator's site.

Data entered in the eCRF that are transcribed from source documents must be consistent with the source documents or the discrepancies must be explained. The Investigator may need to request previous medical records or transfer records, depending on the study. Also, current medical records must be available. Changes or corrections to eCRFs will be made by the Investigator or an authorized member of the study staff according to the policies and procedures at the site.

9.10. Study and Site Closure

The Sponsor or designee reserves the right to close the study site or terminate the study at any time for any reason at the sole discretion of the Sponsor. Study sites will be closed upon study completion. A study site is considered closed when all required documents and study supplies have been collected and a study-site closure visit has been performed.

The Investigator may initiate study-site closure at any time, provided there is reasonable cause and notice is given in advance of the intended termination.

Reasons for the early closure of a study site by the Sponsor or Investigator may include but are not limited to:

- Failure of the Investigator to comply with the protocol, the requirements of the IRB/IEC or local health authorities, the Sponsor's procedures or GCP guidelines.
- Inadequate recruitment of patients by the Investigator.
- Discontinuation of further study intervention development.

9.11. Publication Policy

The conditions regulating dissemination of the information derived from this study are described in the Clinical Trial Agreement.

Appendix 1. Contraceptive Guidance

Female patients of childbearing potential must agree to take appropriate precautions to avoid pregnancy from Screening through 30 days after the last dose of study treatment.

Male patients should use a condom during treatment and through 90 days after the end of systemic exposure to study treatment. If the male patient has a partner that is of child-bearing potential, the partner should also use contraception through 90 days after the end of systemic exposure to study treatment. In addition, male patients must refrain from donating sperm during the study through 90 days after the end of systemic exposure of study treatment. Males who have had a vasectomy qualify as having met the requirement for a highly effective birth control method.

Definitions:

Woman of Childbearing Potential (WOCBP)

A woman is considered fertile following menarche and until becoming post-menopausal unless permanently sterile (see below). If fertility is unclear (e.g., amenorrhea in adolescents or athletes) and a menstrual cycle cannot be confirmed before first dose of study treatment, additional evaluation should be considered.

Women in the following categories are **not** considered WOCBP

1. Premenarchal.
2. Premenopausal female with 1 of the following:
 - Documented hysterectomy.
 - Documented bilateral salpingectomy.
 - Documented bilateral oophorectomy.

For individuals with permanent infertility due to an alternate medical cause other than the above, (e.g., mullerian agenesis androgen insensitivity), Investigator discretion should be applied to determining study entry.

Note: Documentation can come from the site personnel's: review of the patient's medical records, medical examination or medical history interview.

3. Postmenopausal female
 - A postmenopausal state is defined as no menses for 12 months without an alternative medical cause.

- a. A high follicle stimulating hormone (FSH) level in the postmenopausal range may be used to confirm a postmenopausal state in women not using hormonal contraception or hormonal replacement therapy (HRT). However, if patients have less than 12 months of amenorrhea, confirmation of menopause requires more than one FSH measurement.
- Females on HRT and whose menopausal status is in doubt will be required to use one of the non-estrogen hormonal highly effective contraception methods if they wish to continue their HRT during the study. Otherwise, they must discontinue HRT to allow confirmation of postmenopausal status before study enrollment.

Contraception Guidance:

NOTE: There is a potential for encorafenib to induce CYP3A4, which may reduce the effectiveness of hormonal contraception methods. Therefore, the use of at least 1 form of non-hormonal contraception is required for females of childbearing potential during participation in this study.

The contraception guidelines outlined below are adapted from the recommendations related to contraception and pregnancy testing in clinical studies guidance document ([Clinical Trial Facilitation Group Guidelines 2014](#)). Patients must agree to use highly effective methods of contraception if it is mandated locally or when, in the judgment of the Investigator, compliance with acceptable methods is likely to be suboptimal.

The following methods have been classified as being highly effective (i.e., failure rate < 1% per year when used consistently and correctly) in preventing a pregnancy:

- Complete abstinence from heterosexual intercourse during the entire period of risk associated with the study treatments; the reliability of sexual abstinence should be evaluated in relation to the duration of the clinical study and the preferred and usual lifestyle of the patient.
- Combined (estrogen and progestogen containing) hormonal contraception associated with inhibition of ovulation:
 - Oral.
 - Intravaginal.
 - Transdermal.
- Progestogen-only hormonal contraception associated with inhibition of ovulation:
 - Oral.
 - Injectable.
 - Implantable.
- Intrauterine device (IUD).
- Intrauterine hormone-releasing system (IUS).

- Bilateral tubal occlusion.
- Vasectomized partner (considered highly effective provided the vasectomized male has received medical assessment of surgical success and that the male is a female patient's sole sexual partner).

Acceptable birth control methods characterized as having a failure rate of more than 1% per year include:

- Progestogen-only oral hormonal contraception, where inhibition of ovulation is not the primary mode of action.
- Male or female condom with or without spermicide.
- Cap, diaphragm or sponge with spermicide.

Appendix 2. Recommended Dose Modifications for Encorafenib-related* Adverse Events

Severity of Adverse Event	Dose Modifications
New Primary Malignancies	
Non-cutaneous RAS mutation-positive malignancies	Permanently discontinue.
Uveitis	
Grade 1-3	If Grade 1 or 2 does not respond to specific ocular therapy, or for Grade 3 uveitis, withhold encorafenib and binimetinib for up to 6 weeks. 
 • If improved, resume at same or reduced dose. • If not improved, permanently discontinue.
Grade 4	Permanently discontinue encorafenib and binimetinib.
Other Eye Disorders (i.e., non-Uveitis Events)	
Grade 1–2	Maintain dose level of encorafenib and binimetinib and increase frequency of ophthalmic monitoring to at least every 14 days until stabilization or resolution.
Grade 3	Interrupt dosing of encorafenib and binimetinib and refer patient to ophthalmologist within 7 days. 
 1. If resolved to Grade ≤ 1 in ≤ 21 days, resume treatment at 1 reduced dose level of encorafenib and binimetinib. 2. If not resolved to Grade ≤ 1 in ≤ 21 days, permanently discontinue encorafenib and binimetinib and close follow-up with ophthalmic monitoring until stabilization or resolution.
Grade 4	Permanently discontinue encorafenib and binimetinib and immediate follow-up with ophthalmic monitoring until stabilization or resolution.
QTc Prolongation	
QTcF > 500 ms and ≤ 60 ms increase from baseline	1 st occurrence: 
 • Temporarily interrupt dosing of encorafenib until QTcF < 500 ms. Then resume treatment at 1 reduced dose level of encorafenib. 2 nd occurrence: 
 • Temporarily interrupt dosing of encorafenib treatment until QTcF < 500 ms. Then resume treatment at 1 reduced dose level of encorafenib. 3 rd occurrence: 
 • Permanently discontinue encorafenib.
QTcF > 500 ms and > 60 ms increase from baseline	Permanently discontinue.

Severity of Adverse Event	Dose Modifications
Hepatotoxicity	
Grade 2 AST or ALT increased	Maintain encorafenib dose. 
 If no improvement within 4 weeks, withhold encorafenib until improved to Grade 0-1 or to pretreatment/baseline levels and then resume at the same dose.
Grade 3 or 4 AST or ALT increased	See Other Adverse Reactions
Dermatologic (Except Hand-foot Skin Reactions)	
Grade 2	If no improvement within 2 weeks, withhold until Grade 0-1. Resume at same dose if first occurrence or reduce dose if recurrent.
Grade 3	Withhold until Grade 0-1. Resume at same dose if first occurrence or reduce dose if recurrent.
Grade 4	Permanently discontinue.
Hand-foot Skin Reaction (HFSR)/Palmar-plantar Erythrodysesthesia Syndrome (Dose Adjustment for Encorafenib ONLY)	
Grade 1	Maintain dose of encorafenib. Promptly institute supportive measures, such as topical therapy, for symptomatic relief. Give instruction on life-style modifications.
Grade 2	1 st occurrence: 
 Maintain dose of encorafenib and HFSR should be closely monitored. Promptly institute supportive measures, such as topical therapy, for symptomatic relief. Give instruction on life-style modifications. If no improvement \leq 14 days, interrupt dosing of encorafenib until resolved to Grade \leq 1. Resume treatment with encorafenib at current dose level. Continue supportive measures, such as topical therapy, for symptomatic relief. Give instruction on life-style modifications. Additional occurrence: 
 Treatment with encorafenib may be maintained or interrupted based upon the Investigator's discretion. Continue supportive measures, such as topical therapy, for symptomatic relief. Give instruction on life-style modifications. If interrupted dosing of encorafenib per Investigator's judgment, interrupt until resolved to Grade \leq 1. Resume treatment with encorafenib at the same dose

Severity of Adverse Event	Dose Modifications
	level or 1 reduced dose level based upon the Investigator's discretion.
Grade 3	
1st or additional occurrence: Interrupt dosing of encorafenib until resolved to Grade ≤ 1. Promptly initiate supportive measures, such as topical therapy, for symptomatic relief. Give instruction on life-style modifications. Reassess the patient weekly. Then resume treatment at one reduced dose level of encorafenib.
 
 Consider referral to dermatologist and manage HFSR per dermatologist's recommendation. 
> 3rd occurrence: Interrupt dosing of encorafenib until resolved to Grade ≤ 1, decision to resume treatment with encorafenib at one reduced dose level or permanently discontinue encorafenib should be based upon the Investigator's discretion.

Nausea/Vomiting	
Grade 1-2	Maintain dose level of encorafenib and binimetinib. Promptly institute antiemetic measure.
Grade 3	
Interrupt dosing of encorafenib and binimetinib until resolved to Grade ≤ 1. Then resume treatment at 1 reduced dose level of encorafenib. Resume treatment with binimetinib at the current dose if, in the judgment of the Investigator, the toxicity is considered to be unrelated to binimetinib, or at 1 reduced dose level.
 
Note: Interrupt dosing of encorafenib and binimetinib for ≥ Grade 3 vomiting or Grade 3 nausea only if the vomiting or nausea cannot be controlled with optimal antiemetics (as per local practice).

Grade 4	Permanently discontinue encorafenib and binimetinib.
Other Adverse Reactions (including renal, haemorrhage). Additional renal guidance is provided in Section 7.3.9.	
Recurrent Grade 2 or First occurrence of any Grade 3	
Withhold for up to 4 weeks.
 
 If improves to Grade 0-1 or to pretreatment/baseline levels, resume at reduced dose. If no improvement, permanently discontinue.

Severity of Adverse Event	Dose Modifications
First occurrence of any Grade 4	Permanently discontinue or withhold for up to 4 weeks. 
• If improves to Grade 0-1 or to pretreatment/baseline levels, then resume at a reduced dose.• If no improvement, permanently discontinue.
Recurrent Grade 3	Consider permanently discontinuing.
Recurrent Grade 4	Permanently discontinue.

*For adverse events that may be related to both encorafenib and binimetinib, guidance is provided for the other agent also.

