6.7. Dose Modification

6.7.1. General Procedures for Dose Modification

Treatment with encorafenib and binimetinib may be delayed, allowing for resolution of toxicity. Patients may resume treatment if no medical condition or other circumstance exists that, in the opinion of the Investigator, would make the patient unsuitable for further participation in the study. Patients should resume study treatment within 2 weeks of the scheduled interruption, unless otherwise discussed with the Sponsor. The Investigator should contact the Sponsor Medical Monitor to discuss the case of any patient whose treatment has been delayed for more than 2 weeks (14 days) before restarting study treatment.

Instructions for dose modifications and interruptions are outlined in [Appendix 2](#) (encorafenib) and [Appendix 3](#) (binimetinib). Individual decisions regarding dose interruptions and modifications should be made using appropriate clinical judgment in consultation with the Sponsor Medical Monitor, considering relatedness of the AE to the study treatment and the patient's underlying condition. Adverse events that have a clear alternative explanation, or transient (≤ 72 hours) abnormal laboratory values without associated clinically significant signs or symptoms may be exempt from dose-reduction rules as clinically appropriate. Dose interruptions are permitted in the case of medical or surgical events or logistical reasons not related to study treatment (e.g., elective surgery, unrelated medical events, patient vacation, holidays). The reason for interruption will be documented in the patient's study record. All dose modifications are based on the worst preceding toxicity.

Doses of encorafenib and binimetinib may be independently delayed and reduced for toxicity management as outlined in [Table 8](#). The Investigator should refer to and follow the labeled guidance (if applicable) and/or institutional guidelines for the management of toxicities relating to encorafenib and binimetinib. Detailed guidelines can also be found in [Appendix 2](#) and [Appendix 3](#).

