Appendix 3. Recommended Dose Modifications for Binimetinib-related* Adverse Events

Severity of Adverse Event	Dose Modifications
Cardiomyopathy	
Asymptomatic, absolute decrease in LVEF of > 10% from baseline that is also below the LLN	Withhold binimetinib for up to 4 weeks, evaluate LVEF every 2 weeks. Resume binimetinib at a reduced dose if the following are present: 
 • LVEF is at or above the LLN and • Absolute decrease from baseline is 10% or less and • Patient is asymptomatic. If LVEF does not recover within 4 weeks permanently discontinue binimetinib.
Grade 3-4 (Symptomatic congestive heart failure or absolute decrease in LVEF of > 20% from baseline that is also below LLN)	Permanently discontinue binimetinib. Closely monitor LVEF until resolution or up to 16 weeks.
Venous Thromboembolism	
Uncomplicated DVT or PE	Withhold binimetinib. 
 • If improves to Grade 0-1, resume at a reduced dose. • If no improvement, permanently discontinue binimetinib.
Life threatening PE	Permanently discontinue binimetinib.
Serous Retinopathy	
Symptomatic serous retinopathy/ Retinal pigment epithelial detachments	Withhold binimetinib for up to 10 days. 
 • If improves and becomes asymptomatic, resume at the same dose. • If not improved, resume at a lower dose level or permanently discontinue binimetinib.
Retinal Vein Occlusion (RVO)	
Any Grade	Permanently discontinue binimetinib.
Uveitis	
Grade 1-3	If Grade 1 or 2 does not respond to specific ocular therapy, or for Grade 3 uveitis, withhold binimetinib and encorafenib for up to 6 weeks. 
 • If improved, resume at same or reduced dose. • If not improved, permanently discontinue binimetinib.
Grade 4	Permanently discontinue.
Other Eye Disorders (i.e., Non-retinal Events, non-Uveitis Events)	
Grade 1-2	Maintain dose level of encorafenib and binimetinib and increase frequency of ophthalmic monitoring to at least every 14 days until stabilization or resolution.
Grade 3	Interrupt dosing of encorafenib and binimetinib and refer patient to ophthalmologist within 7 days.

Severity of Adverse Event	Dose Modifications

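### The Other Eye Disorders row excludes retinal events in Appendix 3 but not in Appendix 2, so for some retinal events the two appendices give different binimetinib instructions and neither is given precedence

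*Protocol*

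**What the plan says.** **Appendix 2 (encorafenib-related events)** has two eye categories: uveitis, and "Other Eye Disorders (i.e., non-Uveitis Events". There is no row for serous retinopathy or RVO. For Grade 1-2 events in the second category the instruction is "Maintain dose level of encorafenib and binimetinib and increase frequency of ophthalmic monitoring to at least every 14 days until stabilization or resolution". Grade 3 interrupts both drugs and, if the event resolves to Grade 1 or less within 21 days, restarts both one level lower. Grade 4 stops both. A footnote adds: "For adverse events that may be related to both encorafenib and binimetinib, guidance is provided for the other agent also".

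**Appendix 3 (binimetinib-related events)** has the same row with the same actions at each grade, but its heading is "Other Eye Disorders (i.e., Non-retinal Events, non-Uveitis Events". Retinal events have rows of their own. For symptomatic serous retinopathy or retinal pigment epithelial detachment, with no grade stated, the text is "Withhold binimetinib for up to 10 days". Binimetinib then resumes at the same dose if the event improves and becomes asymptomatic; otherwise it resumes at a lower level or stops for good. For RVO of any grade the instruction is to "permanently discontinue binimetinib". Appendix 3 carries the same footnote about the other agent.

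**Section 6.7.1** points to Appendix 2 for encorafenib and Appendix 3 for binimetinib, and says: "Individual decisions regarding dose interruptions and modifications should be made using appropriate clinical judgment in consultation with the Sponsor Medical Monitor". Relatedness of the event is to be considered. The section does not rank the two appendices.

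**The concern.** The actions in the shared row are identical and only the scope differs. Because Appendix 2 excludes nothing but uveitis and has no retinal row, a retinal event falls into its residual eye category by the plain wording. That category gives an explicit binimetinib instruction, which is not the one in Appendix 3.

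Patient safety is at stake first: for the same event, one table continues a drug that the other pauses or ends. Reporting is affected second. The SAP summarises dose reductions and interruptions with their reasons (Section 6.5.3.1), and adverse events leading to interruption, reduction or discontinuation separately for each drug (Section 6.6.1). Those counts would partly reflect which table a site consulted.

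**Working it through.** The plan states no figure on this point to reproduce. The check is a comparison of rows, followed by a rough count of affected patients.

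**Step 1. Binimetinib action by event, read literally, for events that may be related to both drugs.**

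| Event | Appendix 2 | Appendix 3 | Result |
|---|---|---|---|
| Symptomatic serous retinopathy or pigment epithelial detachment, Grade 1-2 | Maintain | Withhold up to 10 days | Conflict |
| RVO, Grade 1-2 | Maintain | Stop permanently | Conflict |
| Symptomatic serous retinopathy, Grade 3 | Interrupt; one level lower if resolved within 21 days | Withhold up to 10 days; same dose if improved and asymptomatic | Conflict |
| RVO, Grade 3 | Interrupt; one level lower if resolved within 21 days | Stop permanently | Conflict |
| Asymptomatic serous retinopathy, Grade 1-2 | Maintain | No eye-specific row | Gap, not a contradiction |

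For serous retinopathy at Grade 4 the rows also differ on their face. Section 6.8 separately lists a Grade 4 event as a reason to stop study treatment, so I put no weight on that case.

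**Step 2. Is there a tie-break?** Section 6.7.1 allocates the appendices by drug, but the Appendix 2 row names binimetinib at every grade. Where Appendix 2 means encorafenib alone, it can say so: its hand-foot skin reaction heading limits the adjustment to encorafenib. No sentence in Section 6.7 or in either appendix says which table governs when they differ.

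**Step 3. Does the re-escalation bar add to this?** Section 6.7.1 bars re-escalation of either drug after a dose reduction for ocular toxicity of Grade 2 or higher. For a Grade 1-2 serous retinopathy that improves, Appendix 2 makes no reduction and Appendix 3 resumes at the same dose, so the bar is not triggered. It matters at Grade 3 under Appendix 2, which reduces both drugs, and for a Grade 2 or higher event that does not improve and is resumed at a lower level under Appendix 3.

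**Step 4. Expected numbers.** Inputs: symptomatic serous retinopathy 8% and RVO 0.1% (protocol Section 2.2.3). Phase 2 enrols up to 100 patients and closes when either cohort reaches 50 (protocol Sections 4.1 and 8.2), so a completed Phase 2 has between 50 and 100. Assumption: the earlier rates apply here.

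- Symptomatic serous retinopathy: 50 × 0.08 = 4, and 100 × 0.08 = 8. Binomial 2.5th to 97.5th percentiles: 1 to 8 for 50 patients, 3 to 14 for 100.
- RVO: 50 × 0.001 = 0.05, and 100 × 0.001 = 0.1 expected. Chance of at least one: 1 − 0.999^50 = 0.049, and 1 − 0.999^100 = 0.095.

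**The case against.** The strongest reply is that the protocol already steers retinal events to Appendix 3. Section 6.7.1 allocates the appendices by drug and asks for relatedness to be weighed. Section 2.2.3 describes serous retinopathy and RVO as class effects of MEK inhibitors, and binimetinib is the MEK inhibitor. The footnote extends guidance to the other agent only for events that may be related to both. An event attributed to binimetinib alone therefore goes to Appendix 3 without conflict. A named row would also usually be read ahead of a residual one, and the dose-limiting toxicity table (Table 7) lists retinal events apart from other eye disorders. Both appendices are titled as recommendations, and the Medical Monitor is to be consulted.

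Most of this stands, and it narrows the point. A reader might infer that Appendix 2 governs binimetinib for every retinal event, or that two sites could take opposite actions after an RVO and be equally compliant. The documents do not support that: the footnote is conditional, and a site opening only Appendix 2 would have passed over the one that Section 6.7.1 names for binimetinib.

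The reply does not remove the mismatch. In a combination trial, attribution to both drugs is an ordinary outcome. For those events the Appendix 2 row speaks to binimetinib directly, and clinical judgment does not tell a site which of two written instructions the protocol intends.

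**Conclusion.** The contradiction is in the text and needs correcting, because it concerns dosing during a recognised toxicity. It is limited to retinal events that may be related to both drugs. For serous retinopathy it covers symptomatic events only.

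If the 8% rate carries over, about 4 to 8 patients would have symptomatic serous retinopathy. Quoting 8 alone would assume full enrolment of 100. Only those whose event may be related to both drugs meet the conflicting text. RVO gives the sharpest conflict but would probably not arise: the chance of any case is about 5% to 10%, before allowing for exclusion criterion 17, which keeps out patients with RVO or current risk factors for it.

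Two larger readings should be resisted. A reader might infer a threat to the trial's conclusions. However, the Phase 2 primary endpoint is the brain metastasis response rate, the Phase 2 dose-modification summaries are descriptive, and the Safety Lead-in decision had already been made when the SAP was written (SAP Section 2). A reader might also infer that the choice of appendix fixes the dose for the rest of treatment. That can follow only where a dose reduction is made.

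Nothing here says which instruction is clinically right.

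**What to change.** Reconcile the eye-disorder rows of Appendices 2 and 3 so that each retinal event (symptomatic and asymptomatic serous retinopathy, pigment epithelial detachment, RVO) has one consistent instruction for encorafenib and one for binimetinib. Alternatively, add a sentence to Section 6.7.1 saying which appendix prevails for which drug when they differ. Narrowing the Appendix 2 heading alone would be incomplete, because retinal events would then have no eye-specific encorafenib instruction. The sponsor's clinical team decides the content.

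The cost is a few lines in a protocol amendment and a notice to sites. No new data, visits or analyses are needed.
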